5. CONCOMITANT MEDICATIONS

Subjects may be treated with other medications as needed in the critical care situation. The treating physician will manage neonates as he/she deems to be in their best interest.

Investigators are required to record all these medications in the eCRF with the only exception of the following drugs, when they are administered for prophylaxis only and not relative to any adverse event:

- Multivitamin or single vitamins (except for vitamin K and vitamin A which must be recorded);
- Probiotics and lactoferrin;
- Nystatin;
- Iron supplements;
- Folic acid;
- Calcium and phosphorus;
- Symeticon;
- Glycerine suppository.

5.1 Permitted concomitant Medications

Any concomitant medication required for the normal care of preterm neonates will be permitted during the study and recorded in the eCRF.

The use of sedative/analgesic medication, as well as the use of atropine, before / during surfactant administration, will be at investigator’s discretion and according to each neonatal intensive care unit (NICU) internal standard practice. If premedication is used, the Investigator should define a protocol (with specification of drugs and dosages) before starting enrollment, which allows for a step-by-step management of pain and sedation for the endotracheal administration of surfactant. Each neonate will be managed according to the pre-defined protocol, and decision on which step of the protocol to apply should be based on neonate’s needs. The same step-by-step protocol should be applied to both treatment arms. The protocol will be provided to the Sponsor.

If caffeine is administered, it should be used in both treatment arms.

5.2 Non-permitted previous and concomitant Medications

1. Surfactant treatment prior to randomization and study treatment administration;
2. Intratracheal administration of any other treatment (e.g. nitric oxide) prior to randomization and study treatment administration;
3. Other investigational drugs or investigational devices under the provisions of a protocol on the same therapeutic target. See [exclusion criteria #10](#).

6. TREATMENT(S)

6.1 Appearance and Content

Poractant alfa (Curosurf[®]) is a standard natural surfactant treatment prepared from porcine lungs for intratracheal administration and containing almost exclusively polar lipids, in particular phosphatidylcholine (about 70% of the total phospholipid content), and about 1% of specific low molecular weight hydrophobic proteins SP-B and SP-C with a total concentration of 80 mg/ml. The drug product is filled in sealed 3.0 ml glass vials

Chiesi Farmaceutici S.p.A. will supply the study medication and also provide the Pharmacist/Investigator with appropriate certificates of analytical conformity.

6.2 Dosage and Administration

6.2.1 Selection of doses in the study

Poractant alfa (Curosurf[®]) will be administered as 200 mg/kg for the first dose and 100 mg/kg for additional doses.

6.2.2 Dosage

Poractant alfa (Curosurf[®]) 2.5 ml/kg (200 mg/kg) sterile suspension in one single intratracheal administration from 30 minutes after birth up to 24 hours after birth.

Poractant alfa 1.25 ml/kg (100 mg/kg) will be used for further re-dosing in both arms (see section [6.2.3.6](#)) up to two repeated doses.

6.2.3 Administration

6.2.3.1 Preparation for surfactant administration

Poractant alfa should be administered by, or under the supervision of, clinicians experienced in intubation, ventilator management, and general care of premature neonates. The neonate should be stabilized before surfactant administration.

Since poractant alfa suspension is refrigerated, before use each vial must be warmed up slowly to room temperature e.g. by placing it in an incubator for about 1 hour or keeping it in hands for 5-10 minutes and gently turned upside down, without shaking, avoiding the formation of foam. Artificial warming methods should not be used.

The entire contents of the vial of poractant alfa suspension should be slowly withdrawn into a 3 or 5mL plastic syringe through a large-gauge needle and the excess poractant alfa discarded. The syringe filled with poractant alfa suspension will be connected directly to LISA thin catheter (CHF 6440) in LISA cohort or attached to a 5-French catheter end-hole inserted into the endotracheal tube (ETT) or to the proximal end of the secondary lumen of a dual lumen ETT in the standard cohort, according to the approved delivery method.

Preparation should also include appropriate equipment such as an oxygen source, appropriately sized bags, face masks, stylet, laryngoscope and suction.

Neonatal team should include at least two people present during the maneuver: one performing the procedure and one additional person who can assist.

Before starting the procedure and throughout it, neonates must have cardiorespiratory monitoring: oxygen saturation and heart rate continuously through pulse oximetry, blood pressure measurement either continuously in presence of an arterial catheter or intermittently if no arterial line is in place.

6.2.3.2 Sedation and analgesia

The use of sedative/analgesic medication, as well as the use of atropine, before/during surfactant administration, will be at investigator's discretion and according to each neonatal intensive care unit (NICU) internal standard.

If premedication is used, the Investigator should define a protocol (with specification of drugs and dosages) before starting enrollment, which allows for a step-by-step management of pain and sedation for the endotracheal administration of surfactant. Each neonate will be managed according to the pre-defined protocol, and decision on which step of the protocol to apply should be based on neonate's needs. The same step-by-step protocol should be applied to both treatment arms. The protocol will be provided to the Sponsor.

A first step could be attempted with a non-pharmacological analgesic technique (sucrose, glucose, holding, swaddling and methods of sensorial saturation).

A pharmacological intervention could be given following a progression in the use of sedatives/analgesics, based on neonate's need. As a guidance, examples of pharmacological interventions which can be used (either alone or in combination) are the following:

- Vagolytic agents (e.g. atropine).
- Sedative/analgesics medications with rapid onset and short duration of action (e.g. fentanyl).

The use of sedation/analgesia and other medications will be carefully recorded along with related information (e.g. date and time of administration, dosage and route) in the relevant section of the eCRF.

6.2.3.3 LISA procedure

LISA-delivery of poractant alfa to the lung will be done via brief insertion of the thin catheter

(CHF 6440) through the mouth into the trachea, while the subject is being supported with NIV. The thin catheter will be provided by the Sponsor ([Figure 1: CHF 6440](#)).

CHF 6440 is a sterile, single-use catheter. It has a working length of 130.0 mm, presents a 1.7 mm Outer Diameter (corresponding to a 5 French OD), with a 1.1 mm Internal Diameter (corresponding to 3.5 French ID) through which the surfactant is delivered. The hole at the distal edge has a diameter of 0.8 mm. It includes a standard polycarbonate mono Luer connection at the proximal end. The Luer is bonded to a reinforced shaft, with the shaft consisting of composite assembly of an overcoat / jacket, a braided woven stainless steel, and a Pebax liner. The Pebax leading tip of the device presents a rounded and soft distal edge to provide an atraumatic lead for the catheter during insertion via mouth. Printed depth markings on the outer surface of the shaft provide visual guide to the depth of device insertion during clinical procedure. Do not manipulate, kink and bend the catheter prior to its insertion. Check the presence of the ring markings prior to the insertion of this catheter.

The neonate will be placed supine with the head in neutral position before the onset of the procedure. The procedure should be performed with the NIV remaining in situ during surfactant administration. Poractant alfa should be administered by, or under the supervision of clinicians experienced in intubation of premature neonates. The investigators' site staff will be trained during the Investigators' meeting and site initiation visits in performing the LISA technique through a specific informative video as well as the provision of a specific mannequin **Error! Hyperlink reference not valid.** designed to facilitate the training of healthcare professionals in the initiation of proper care and resuscitation of preterm infants.

Following direct laryngoscopy, the catheter will be introduced orally and inserted through the vocal cords into the trachea to the desired depth of 1-2 cm, the laryngoscope will be carefully removed while the catheter is secured by the fingers of the neonatologist/investigator, who will finally close the neonate's mouth. The correct position of the catheter into the trachea will be confirmed by the visualization of tip depth markings and by the tip-to-lip measurement. The thin catheter presents three different ring markings close to the tip, equal to 1, 2 and 3 cm ([Figure 1C](#)) and helpful to address the depth of insertion beyond the vocal cords. Moreover, the catheter presents markings going from 5 to 9 cm for the tip-to-lip measurement, which represents the standard method to estimate the correct position also of the ETT [\[23\]](#).

After having confirmed the correct position of the catheter into the trachea, the syringe filled with poractant alfa suspension will be connected to the Luer of the catheter and poractant alfa will be instilled over 0.5-3 minutes with careful observation of the neonate's continuous spontaneous breathing. Once the surfactant is administered, the catheter will be removed. Before removing the LISA catheter, it should be fully cleared of surfactant with some additional air. After completion of surfactant administration, ventilatory support may require transient adjustments. Airways suction should not be performed for 1 hour after surfactant instillation, unless signs of significant airway obstruction occur.

If on the first attempt the catheterization of the trachea is not possible within 30 seconds, the laryngoscope should be removed and if required neonate's recovery allowed. Then a second

attempt should be performed for a total number of 3 attempts.

Details of the procedure as well as neonate's vital signs and any occurring adverse event will be recorded according to the time points of the protocol by the team member assisting or observing the procedure.

Figure 1: CHF 6440

Figure 1A
CHF 6440 Full View

Figure 1B
Close-up on CHF 6440 Components

a) Standard Luer

b) Rounded and Soft Tip

[figure not shown]

Figure 1C
Close-up of Markings Present on CHF 6440 Shaft

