6.2.3.4 Conventional Intubation, surfactant administration and brief ventilation

As standard control treatment, neonates spontaneously breathing and stabilized on NIV will receive surfactant via ETT using an approved method of administration, connecting the syringe filled with poractant alfa suspension to:

- a 5-French end-hole catheter inserted into the ETT
or
- the proximal end of the secondary lumen of a dual lumen ETT.

The standard ETT has markings along the side to help identifying the correct distance from the tip of the tube.

Following direct laryngoscopy, the ETT will be inserted through the vocal cords into the trachea to the desired depth. The laryngoscope will be then carefully removed. The correct ETT position into the trachea will be confirmed by the visualization of tip depth markings and by the tip-to-lip measurement. The tube position could be checked by auscultation of the chest to ensure equal aeration of both lungs, observation of chest movement synchronous with positive pressure inflation, enhancement of vital signs, absence of stomach distension while ventilation, and where possible, with the measurement of end tidal CO₂ by colorimetric system on the ETT. Once the tube position is confirmed, the ETT will be secured with adhesive tape or other ways according to the NICU policy.

After administration, manual ventilation can be continued, or the neonate can be connected to the ventilator, or the neonate can be immediately extubated and placed again on NIV. Do not suction airways for 1 hour after surfactant instillation unless signs of significant airway obstruction occur.

If connected to the ventilator, extubation should be performed within one hour after surfactant administration and then the neonate placed again on NIV.

Details of the procedure as well as neonate's vital signs and any occurring adverse event will be recorded according to the time points of the protocol by the team member assisting or observing the procedure.

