9. SAFETY ASSESSMENTS

The following variables will be used to describe the safety of the two procedures:

During procedure for surfactant administration

- Number and percentage of neonates with AEs starting during overall procedure for surfactant administration;
- Number and percentage of neonates with AEs starting during overall procedure for surfactant administration judged related to the procedure;
- Number of AEs occurring during overall procedure for surfactant administration requiring either oxygen alone or an increase in FiO₂ without the need for escalation of invasive or non-invasive ventilator support;
- Number of AEs starting during overall procedure for surfactant administration requiring administration of manual (bag and mask) pressure positive ventilation and related duration of ventilation (non- invasive ventilation);
- Number of AEs starting during overall procedures for surfactant administration requiring endotracheal intubation and related duration of intubation (invasive ventilation);
- Number of AEs starting during overall procedures for surfactant administration requiring circulatory support including administration of crystalloids;
- Number of AEs starting during overall procedures for surfactant administration requiring cardiopulmonary resuscitation including administration of cardiac massage or adrenaline.

After first administration

- Number and percentage of neonates with failed 1st attempt to insert the CHF6440/ETT;
- Number of attempts to the first successful insertion;
- Number of device misallocation (esophageal insertion);
- Number of maneuvers discontinued due to neonate's severe destabilization;
- Duration of the whole procedure (starting from the insertion of laryngoscope up to the removal of the catheter or ETT);
- Duration of surfactant administration (min);
- Heart rate (HR) and respiratory rate (RR) (0, 5, 15 and 30 min, 1 hour, 6 and 12 hours after administration);
- Systolic, diastolic, and mean blood pressure (SBP/DBP/ MBP) (15 and 30 min, 1 hour, 6 and 12 hours after administration);
- Premature Infant Pain Profile (PIPP) score [26] (end of surfactant administration).

During the study

- AEs, including incidence of major neonatal complications of prematurity (listed in [APPENDIX III](#)) and adverse drug reactions (ADRs);
- Blood pressure (SBP, DBP, MBP) at 24, 48, 72, 120 hours post-administration;

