12. STATISTICAL METHODS

12.1. Sample Size

No primary efficacy endpoint was defined in this study since the main objective is to describe the overall safety and efficacy profile of administering poractant alfa with two different

procedures: LISA technique or conventional administration with endotracheal tubes and brief invasive ventilation. A total of 150 neonates will be randomized in the study with a ratio 2:1 to LISA arm (i.e. 100) and conventional administration arm (i.e. 50).

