12.3.5. Safety variables

Adverse Events and Neonatal Morbidities

- Number and percent of neonates reporting AEs started during procedure for surfactant administration as well as AEs started during the procedure and judged related to the procedure will be summarized by treatment group.

For LISA group, any AE assessed as related to CHF 6440 catheter will be considered procedure-related.

These events will be also summarized by treatment group based on action required, if any (i.e. supplementary oxygen or transient increase in FiO₂, manual positive pressure ventilation, endotracheal intubation, administration of, crystalloids, or cardiopulmonary resuscitation or administration of adrenaline). The duration of endotracheal intubation and positive pressure ventilation will be

summarized as well.

A subgroup analysis of AEs during procedure for surfactant administration will be performed based on the use of sedation and/or analgesia (Yes/No).

- Incidence of AEs including neonatal complications of prematurity (see [APPENDIX III](#) for complete list), related AEs (ADRs), serious AEs (SAEs) and AEs leading to death will be summarized by treatment group both in term of frequency of neonates with at least one AE and in term of frequency of AEs (number of events). All the aforementioned categories of AEs will be summarized by System organ Class (SOC) and Preferred Term (PT).
- Frequency of neonates with major neonatal morbidities at discharge or 40 weeks PMA (whichever comes first) will be summarized by treatment group.

Vital Sign

- Vital signs parameters (SBP, DBP MBP, HR and RR) will be summarized as absolute and the change from baseline (pre-procedure) by treatment group using descriptive statistics.

Pain assessment

- PIPP score will be summarized by treatment group by means of descriptive statistics.

First administration

- Number of 1st failed attempt to insert the catheter/ETT will be summarized by treatment group. Percentage of neonates with 1st failed attempt will be compared between group using the Cochran-Mantel-Haenszel adjusted for gestational age group. The CMH adjusted difference with its 95% CI will be presented.
- Number of attempts to the first successful insertion will be summarized by treatment group by means of descriptive statistics.
- Number of device misallocation (i.e., esophageal intubation) will be summarized by treatment group by means of descriptive statistics.

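### Failed first attempt is tested between arms, but a 30-second stopping rule is written for LISA only, so the comparison is not like-for-like as planned

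*Protocol*

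**What the plan says.** **LISA arm (Protocol 6.2.3.3).** The instruction begins "If on the first attempt the catheterization of the trachea is not possible within 30 seconds". The laryngoscope should then come out, the neonate should recover if necessary, and a second "attempt should be performed for a total number of 3 attempts".

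**Control arm (Protocol 6.2.3.4).** The matching step reads "Following direct laryngoscopy, the ETT will be inserted through the vocal cords into the trachea to the desired depth". The section gives neither a time limit nor a maximum number of attempts, and no other section supplies one.

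**Variable (Protocol synopsis and section 9).** One variable covers both arms: "Number and percentage of neonates with failed 1st attempt to insert the CHF6440/ETT". The protocol does not define an attempt or a failed attempt.

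**Analysis (Protocol synopsis and section 12.3.5).** "Percentage of neonates with 1st failed attempt will be compared between group using the Cochran-Mantel-Haenszel adjusted for gestational age group". The section adds: "The CMH adjusted difference with its 95% CI will be presented". The number of attempts to first successful insertion is only summarized.

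**Data collected.** Section 9 lists the duration of the whole procedure and of surfactant administration. Neither section 9 nor section 7.1.2 lists times for individual attempts. The flowchart (Table 2) was not available in the text reviewed.

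**The concern.** The two procedure sections are otherwise closely parallel: direct laryngoscopy, insertion through the cords, a check of depth markings and tip-to-lip distance, and an observer who records the details. The stopping rule stands out because it appears on one side only.

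Take an insertion that needs 45 seconds. If the protocol is followed, the LISA operator stops and starts again. Nothing written stops the ETT operator from completing the same insertion. On the natural reading, the first neonate has a failed first attempt and the second does not.

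First-attempt failure is one of the safety variables that the protocol formally compares rather than only summarizes. A difference could be read as one technique being harder to carry out when part of it comes from the stopping rule. Wording in the SAP could settle what counts as failed. Without attempt times from both arms, it could not restore a like-for-like comparison.

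**Working it through.** The protocol gives no expected failure rate, effect size or power for this variable, so there is no figure to reproduce. The check below shows how large the artefact could be.

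**Inputs**
- From section 12.1: 150 neonates randomized 2:1, that is 100 LISA and 50 ETT.
- Assumed: *p*, the true first-attempt failure rate without a time limit, equal in both arms, at 10%, 20% or 30%.
- Assumed: *x*, the share of otherwise successful first attempts that last over 30 seconds, at 5%, 10% or 20%.
- Assumed: every such LISA attempt is stopped and counted as failed, and every such ETT attempt runs on and succeeds.
- Gestational age strata are ignored.

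**Step 1: spurious difference.** The observed LISA failure rate is *p* + (1 − *p*)*x*; the ETT rate stays at *p*. The excess is (1 − *p*)*x*. At *p* = 20%:
- *x* = 5%: 0.80 × 0.05 = 4 points
- *x* = 10%: 0.80 × 0.10 = 8 points
- *x* = 20%: 0.80 × 0.20 = 16 points

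**Step 2: precision.** With 20% failure in both arms, the 95% CI half-width is 1.96 × √(0.20 × 0.80 × (1/100 + 1/50)) = 1.96 × √0.0048 = 13.6 points.

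**Step 3: chance of a significant result against LISA.** The normal approximation for two proportions is used at two-sided 5%. For *p* = 20% and *x* = 10%:
- Pooled rate: (50 × 0.20 + 100 × 0.28)/150 = 0.253
- Null SE: √(0.253 × 0.747 × 0.03) = 0.0753
- Alternative SE: √(0.20 × 0.80/50 + 0.28 × 0.72/100) = 0.0722
- Φ((0.08 − 1.96 × 0.0753)/0.0722) = Φ(−0.94), about 17%

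Without the artefact, the chance in that direction is 2.5%.

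| True failure *p* | Excess at *x* = 5 / 10 / 20% (points) | Chance of a significant excess in LISA |
|---|---|---|
| 10% | 4.5 / 9 / 18 | 10.5 / 28 / 74% |
| 20% | 4 / 8 / 16 | 7.5 / 17 / 52% |
| 30% | 3.5 / 7 / 14 | 6 / 13 / 38% |

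**Step 4: after the fix.** If success in both arms means placement within the same 30 seconds, the slow ETT placements also count as not achieved in time. Both arms then have rate *p* + (1 − *p*)*x*, and the spurious difference is zero. The sample size does not change.

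**The case against.** **Nothing in the protocol makes a stopped attempt a failed one.** The 30-second text is a procedural instruction, not an endpoint rule, and the operational definition of a safety variable may properly sit in the SAP or the eCRF instructions. This stands, and the missing definition is not itself the point. The one-sided stopping rule, however, is in the protocol's own procedure, and the listed data would not let an analyst undo it later.

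**Silence on ETT does not mean unlimited attempts.** Operators are experienced in intubation, or supervised by someone who is, and may follow a local limit that the protocol does not record. This also stands. It means that the size of any bias, and strictly even its direction, cannot be established from the document.

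**The trial compares two procedures, and the 30-second rule belongs to one of them.** Failure under each procedure as delivered is a legitimate quantity and should still be reported. It answers a different question from ease of placement, and the tested comparison should say which one it addresses.

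**The stakes are modest.** The study is described as explorative, defines no primary efficacy endpoint and has many safety variables. The likely bias also runs against the sponsor's own device. This limits the importance of the point but does not remove it.

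**Stronger readings that do not hold.** A reader might infer that LISA failures are inflated by definition. The documents do not support that, because no definition exists and ETT practice is unrecorded. A reader might also infer that the number of attempts is biased in the same way. There, a time limit would raise the LISA count while the cap of three would truncate it, so the net direction is unknown. That variable is not tested.

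**Conclusion.** The point holds as a cheap improvement, not as a serious flaw. As written, the CMH comparison of first-attempt failure is not like-for-like, because a stopping time is stated for one arm only. Bias against LISA is likely if attempts stopped at 30 seconds are counted as failed and ETT attempts are allowed to continue.

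At a 20% true failure rate, the illustrative excess is 4-16 points against a CI half-width of about 13.6 points. Across the wider assumed range it is 3.5-18 points. The effect is small if few attempts pass 30 seconds and material if 10-20% do. The rates are assumptions, and the protocol offers nothing with which to choose among them.

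**What to change.** 1. Record the start and end time of each insertion attempt in both arms.
2. For the between-arm comparison, define first-attempt success identically: correct tracheal placement on the first laryngoscopy within one common elapsed time. Position may be confirmed after the laryngoscope is removed, because both procedure sections describe that order. The analysis cut-off should be no longer than the shortest stopping time in use in either arm, since attempts stopped earlier have no observed outcome beyond that point.
3. Report failure under each arm's own procedure descriptively alongside it.
4. Reconcile sections 6.2.3.3 and 6.2.3.4 for analysis purposes, stating whether any limit on time or number of attempts applies to ETT insertion. Which clinical limit should apply, if any, is outside this review.

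Defining failure only as laryngoscope removal without confirmed placement would not be enough. LISA operators are told to remove it at 30 seconds, so the asymmetry would remain, and confirmation follows removal in both arms.

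The cost is a few eCRF time fields, filled in by the team member who already records the procedure, and some analysis wording. Treatment and sample size are unchanged.
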